1. SYNOPSIS

Trial Title	Pill-in-Pocket Oral Anticoagulation: Responding to Atrial Fibrillation Episodes Guided by Continuous Rhythm Monitoring and Smartphone Alerts		
Internal ref. no. (or short title)	RESPOND-AF		
Trial registration	Clinicaltrials.gov		
Sponsor	Oxford University Hospitals NHS Foundation Trust		
Funder	Medtronic Limited		
Clinical Phase	Feasibility study		
Study Design	Investigator-initiated single centre feasibility study		
Study Participants	
Participants will be recruited from Cardiology outpatient clinics and outpatient lists for DC Cardioversion, as well as those presenting for the first time with recent onset AF to Emergency Department or Acute Medical Unit.
 
Those recruited will be aged 18 years or above with non-valvular paroxysmal atrial fibrillation or persistent AF with a rhythm control strategy. They will have to own a smartphone with operating system compatible with the My Carelink Heart application by Medtronic and be willing and able to use the application. They must fulfill the inclusion criteria listed later in this protocol and on the consent form.
		
Sample Size	50 subjects		
Planned Study Period	24 months		
	Objectives	Outcome Measures	Timepoint(s)
Primary	
Primary Objective
 
To investigate the reduction in oral anticoagulation (OAC) utilization during follow-up.
	
Primary Outcome Measures
 
Calculate the proportion of time off anticoagulation
	
During follow-up (minimum 13 months)

Secondary	
Secondary Objectives
 
1. Thromboembolic events (ischaemic stroke, transient ischaemic
	
Secondary Outcome Measures
 
1. Calculate the rate of ischaemic stroke, TIA and systemic embolism in
	
1. During follow-up (minimum 13 months)

	
attacks (TIA) and systemic embolism)
 
2. Major bleeding
 
3. Minor bleeding
 
4. Any stroke (ischaemic, haemorrhagic or undermined)
 
5. All-cause mortality
 
6. Protocol adherence
 
7. To assess response time from AF episode onset to patient starting as-required OAC
	
patients on as-required OAC
 
2. Calculate the rate of major bleeding in patients on as-required OAC
 
3. Calculate the rate of minor bleeding in patients on as-required OAC
 
4. Calculate the stroke rate (ischaemic, haemorrhagic or undetermined)
 
5. Calculate the rate of all-cause mortality in patients on as-required OAC
 
6. Calculate the percentage of daily automatic transmissions and percentage of patients that restart OAC within 24 hours of the smartphone-alert.
 
7. Time from AF episode onset to detection, time to alerts being sent and acknowledged and OAC being taken by the participant. Proportion of missed AF episodes, transmissions or alerts.
	
2. During follow-up (minimum 13 months)
 
3. During follow-up (minimum 13 months)
 
4. During follow-up (minimum 13 months)
 
5. During follow-up (minimum 13 months)
 
6. During follow-up (minimum 13 months)
 
7. During follow-up (minimum 13 months)

Intervention(s)	
As-required oral anticoagulation (OAC):
 
 • Initiate OAC if continuous AF episodes longer than 1 hour or total AF burden of more than 60 minutes (>4.2%) over a 24-hour period. 
 ○ Dabigatran ○ Rivaroxaban ○ Apixaban 		

	
○ Edoxaban• Discontinue OAC if freedom over a consecutive 30-day period from: (1) AF episodes longer than 1 hour, and (2) AF burden more than 60 minutes in any 24-hour period.
--	--

CONFIDENTIAL

2. ABBREVIATIONS

AE	Adverse event
AF	Atrial fibrillation
AR	Adverse Reaction
AE	Adverse event
CI	Chief Investigator
CRF	Case Report Form
CRT	Cardiac Resynchronisation therapy
CT	Clinical Trials
CTA	Clinical Trials Authorisation
DOAC	Direct oral anticoagulant
GCP	Good Clinical Practice
GP	General Practitioner
HRA	Health Research Authority
ICD	Implanted Cardioverter-Defibrillator
ICM	Implanted Cardiac Monitor
ICF	Informed Consent Form
IRB	Independent Review Board
NHS	National Health Service
OAC	Oral anticoagulation
RES	Research Ethics Service
PI	Principal Investigator
PIL	Participant/ Patient Information Leaflet
PPG	Photoplethysmography
R&D	NHS Trust R&D Department
REC	Research Ethics Committee
RSI	Reference Safety Information
TIA	Transient ischaemic attack
SAE	Serious Adverse Event
TMF	Trial Master File

3. BACKGROUND AND RATIONALE

Disease burden: Atrial fibrillation (AF) is the most common sustained arrhythmia affecting millions of people worldwide, leading to significant morbidity and mortality.⁽¹⁾ It is associated with a 5-fold increased risk of ischaemic stroke⁽²⁾, accounting for 20-25% of all strokes which are generally more severe and disabling than non-AF related strokes.⁽³⁾ OAC remains the cornerstone of AF management: it reduces by two-thirds the risk of stroke, but at the expense of major bleeding (1 in 25 patients per year).^(1, 4)

Clinical Challenge: Risk scores that inform anticoagulation decisions, such as the CHA₂DS₂-VASc score, do not incorporate AF temporal patterns or burden and are based solely on co-morbidities.⁽¹⁾ If the predicted yearly stroke rate is above 1%, there is a net clinical benefit of OAC.⁽⁵⁾ Once OAC is initiated, patients are committed to lifelong anticoagulation regardless of the number or duration of AF episodes.

Current risk scores may overestimate the stroke risk in patients with paroxysmal atrial fibrillation (PAF), low AF burden and short episodes. A meta-analysis of almost 100,000 patients with AF suggests that both the adjusted and unadjusted stroke and mortality risks are higher in non-Paroxysmal AF than in Paroxysmal AF.⁽⁶⁾ Moreover, in a study of 21,768 non-anticoagulated patients with AF detected by cardiac implantable electronic devices, longer AF episode duration was associated with increased thromboembolic risk. Patients with intermediate CHA₂DS₂-VASc score (1-3) and AF episodes lasting less than 23.5 hours had a yearly stroke rate below 1%.⁽⁷⁾ Therefore, indefinite OAC may expose patients with shorter, infrequent AF episodes to a high bleeding risk with limited benefit in stroke risk reduction, in particular those with low-to-moderate risk.

Biological plausibility: Interrogation of more than 9,000 patients with cardiac implantable electronic devices (CIEDs) showed a seventeen-fold increase in the odds of having a stroke in the first 5 days after an AF episode which returns to baseline at 30 days.⁽⁸⁾ This may be explained by both atrial stunning —transient disruption of atrial and atrial appendage contractility — following restoration of sinus rhythm, and an increase in thrombogenesis, from platelet activation and thrombin generation during AF episodes.. Atrial stunning occurs irrespective of mode of cardioversion (spontaneous, pharmacological or electric),⁽⁹⁻¹²⁾ and gradually improves over time if sinus rhythm is restored.^(13, 14) In patients undergoing direct current cardioversion, recovery of atrial mechanical function is strongly influenced by the duration of AF episodes.⁽¹⁴⁾ Recovery within 24 hours was observed in patients with AF episode duration of less than two weeks; recovery increased to one month in those with documented AF lasting for more than 6 weeks.⁽¹⁵⁾

Evidence gap: “As-required” OAC, guided by continuous rhythm monitoring, may be an alternative management strategy in patients with paroxysmal AF and persistent AF on a rhythm-control strategy who have short, infrequent episodes. OAC is started at the onset of an AF episode and continued for the duration of the episode and for a period afterwards. This may offer the same thromboembolic protection as continuous OAC, whilst at the same time reducing cost and bleeding complications.

As-required OAC: Four small feasibility studies have used an implantable cardiac monitor (ICM, e.g. Medtronic LINQ and Reveal XT) to guide “as required” OAC in low-to-moderate risk patients.⁽¹⁶⁻¹⁹⁾ Although the authors concluded that this strategy appears safe, reducing both OAC utilisation and

bleeding, none of these studies were adequately powered to assess for rate of thromboembolic events. Our research group therefore conducted a systematic review and meta-analysis³² of studies using rhythm monitoring (intermittent and continuous) to guide OAC. Across 8 studies and a total of 711 patients on an intermittent anticoagulation regime, the annualised mortality and ischaemic stroke rates per patient-year of follow-up were very low, 0.024 (95% CI [0.018–0.051]) and 0.005 (95% CI [0.002–0.012]), respectively.

A significant limitation seen in studies using continuous rhythm monitoring (ICMs or cardiac implantable electronic devices) was the large volume of data that required adjudication and potential delays between episode detection and restarting OAC — patients had to be contacted by telephone.⁽¹⁶⁻¹⁹⁾ In REACT.COM, during a mean follow-up of 1.2 years, 59 patients generated 24,000 manual transmissions. These limitations in technology and methodology hindered any attempts at a large RCT or incorporation into routine clinical practice.

Innovations in digital health technology may lead to a paradigm shift: personalised treatment for patients with AF. The LINQ II ICM™ (Medtronic, MN, USA) with True-rhythm now incorporates P-wave evidence which significantly reduces the number of false positives whilst still maintaining a very high positive predictive value for AF episodes.^(20, 21) It is also now equipped with low-energy Bluetooth wireless technology that connects directly with users' smartphones, allowing transmission of data to the physicians' web portal (CareLink™) without needing a home monitor. This opens the possibility of real-time, automated notifications to patients informing them of the onset of an AF episode.

Our research group at Oxford University Hospitals, UK have developed a patient messaging software to facilitate sending alerts to patients, which patients can respond to. We confirmed the feasibility of this closed-loop alert system in the recent SMART-ALERT study (discussed below).

In the RESPOND-AF study, patients will have a LINQ II ICM implant. If the ICM picks up an episode of AF, this transmission will trigger our software to send an SMS alert to the patient. This alert will inform them of the AF episode, therefore prompting them to restart their oral anticoagulation. This closed-loop alert system will allow for reduced time from AF episode detection to initiation of OAC and facilitates remote monitoring workflow.

Figure 1. LINQ II implantable cardiac monitor (ICM) connectivity

The duration of AF episodes that start to increase thromboembolic risk (and thus merit OAC) remains unclear. The arbitrary diagnostic cut-off of 30 seconds of AF on an electrocardiogram was introduced as an inclusion criterion in clinical trials and it is still used to diagnose AF. Continuous rhythm monitoring with cardiac implantable electronic devices allows detection of atrial high-rate episodes (AHRE)/subclinical AF and assessment of episode duration and stroke risk. In published trials, stroke risk began to increase after subclinical AF episodes longer than 5 minutes in the MOST trial, after 1 hour in SOS, 5.5 hours in TRENDS, and 24 hours in the Veteran Affairs study and ASSERT (post-hoc analysis).⁽²²⁻²⁶⁾ The data therefore suggest that longer episodes (hours) rather than shorter episodes (minutes) increase the risk of thromboembolism.

The 2020 ESC AF guideline acknowledges the uncertainty between the duration of subclinical AF episode and the thromboembolic risk but highlights that longer episodes (>24hours) have a higher risk of thromboembolic complications and progression to clinical AF.⁽²⁷⁾ Furthermore, it states that OAC may be considered in patients with high stroke risk and subclinical AF episodes longer than 24h, pending data from ongoing RCTs.^(28, 29)

These RCTs (ARTESIA²⁸ study and NOAH-AFNET 6²⁹) have since reported. They were designed to assess the treatment of AHRE/subclinical AF episodes of >6 minutes (and <24 hours in ARTESIA) with a direct-acting oral anticoagulant. In ARTESIA, apixaban resulted in a lower risk of stroke or systemic embolism than aspirin, but a higher risk of major bleeding. In NOAH-AFNET 6, edoxaban did not lead to a significant reduction in the composite endpoint of stroke, systemic embolism, or cardiovascular death compared with placebo, and led to a higher incidence of a composite of death or major bleeding. A meta-analysis of these two studies⁽³³⁾ has demonstrated an overall significant reduction in ischaemic stroke in anticoagulated patients, with no reduction in cardiovascular death or all-cause mortality, and a significant increase in major bleeding. These results would appear to support the ESC guideline to consider OAC in this subclinical AF patient group.

In the RESPOND-AF study, we have chosen a pragmatic cut-off of a continuous AF episode longer than one hour and/or a daily AF burden of more than 1 hour during a 24-hour period (>4.2%) to initiate OAC. Built into our protocol is a target for participants to commence OAC within 24 hours of AF onset, and no later than 48 hours.

Preliminary data: Our research group conducted a review of patients with AF and complex cardiac devices treated at Oxford University Hospitals, to assess potential reduction in OAC usage if they were treated with an “as-required” OAC approach. Retrospective analysis of 331 patients identified 106 with AF, corresponding to a total follow-up period of 393 patient-years. An “as-required” strategy of OAC for 1 month following an AF episode longer than 1 hour (as per RESPOND-AF protocol) would lead to a significant reduction of time on OAC: 86.5% reduction for paroxysmal AF patients, and 46.3% reduction in recurrent persistent AF patients.⁽³⁰⁾

3.1 SMART-ALERT study

SMART-ALERT study: (*study complete, analysis and preparation of manuscript ongoing*) In this study our research group aimed to assess the feasibility and robustness of: (1) the closed-loop system

using LINQ II™ ICM remote monitoring to detect AF, (2) our custom software platform (discussed in section below) to alert patients of the AF episode, (3) of patients acknowledging receipt of the alert.

We also assessed the accuracy of wearable devices during the follow-up period: the Apple Watch and the SkyLabs CART-I Smart Ring. We used the LINQ II as the gold standard comparator of their accuracy.

Preliminary results: We recruited 50 patients with known frequent episodes of AF. Early results indicate this approach is reliable and accurate. On interim analysis, the median time from AF episode detection to SMS alert was 183 minutes (3.1 hours). The median time from SMS alert to patient reply was 5.1 minutes. Only 1 episode took longer than 24 hours for the patient to reply. On 3 occasions there was no patient reply. The median total time from AF episode detection to patient reply was 296.5 minutes (4.9 hours) and 94% of replies occurred within 24 hours.

In the context of the RESPOND-AF study, a median time of 4.9 hours from AF episode detection to commencing oral anticoagulation would be deemed safe and appropriate. In fact, most of the patient responses in SMART-ALERT occurred within 1 - 3 hours.

These timings represent the combined results from versions 1.0, 2.0 and 3.0 of our custom software programme. The earlier versions had intermittent technical issues, with periods of the software programme crashing and not automatically restarting. On these occasions manual restart of the software programme was required. This resulted in occasions with delays to SMS alerts being sent to patients while versions 1.0 and 2.0 of the software programme were running. Version 3.0 did not require any manual restart while operational, correcting the previous technical issues.

We are undertaking further analysis of the performance of each version of the software programme. We expect that the detection and response times will be much improved for version 3.0 of the software programme.

[figure not shown]

Figure 2. Preliminary results of interim analysis A) Time to AF episodes to SMS alert, B) time from SMS alert to acknowledgment, total time

3.2 Custom patient notification programme

Custom Software: Our patient messaging software was developed in-house at Oxford University Hospitals in collaboration with BrainLogic Ltd software development company. The programme is designed to monitor the Medtronic Carelink™ records of our patient cohort every 5 minutes continuously, and alert them via SMS message when AF episodes are detected by the LINQ II™ ICM. The patient is prompted to acknowledge the alert with a reply SMS, and this response is logged by our software programme.

During the SMART-ALERT study the custom software had two major updates to its code. These were in response to issues with delays to SMS alerts being sent to patients and minor ad-hoc updates due to CareLink™ and Google Chrome™ browser updates and/or changes. Version 3.0 ran seamlessly from January 2023 until study closure in June 2023 without any human intervention or manual restarting required. We continue to observe and analyse participant transmissions in a post-study clinic for patients who have completed follow-up and agreed to ongoing remote monitoring with the implanted cardiac monitor.

BrainLogic will continue to host and manage the running of the software. We also maintain communication with the Medtronic engineering team regarding how our software interacts with the Carelink™ system.

The overall objective of the RESPOND-AF study is to assess the feasibility of an automated approach to “as-required” anticoagulation. We are not assessing the performance of the LINQ II device or of our messaging software, which was assessed extensively during the previous SMART-ALERT study.

RESPOND-AF is not being carried out for the purposes of seeking CE-marking for our patient messaging software, and we do not intend to commercialise it. The software was developed in-house to be used solely as a research tool for patients recruited at our single-site research institution and will not be used outside of the remit of this study.

3.3 Public and patient involvement

Patient-public involvement: We conducted a survey in 320 patients with a diagnosis of AF in collaboration with the AF association. In this survey, a quarter of patients forget to take their OAC at least once a week, one third has experienced side effects from taking OAC and 70% worry about bleeding complications. Importantly, it highlights that patients would welcome alternative stroke prevention strategies, and more than half (55%) would choose an as-required OAC guided by an ICM if this strategy was deemed safe.

An ICM implant does not appear to be a barrier to recruitment in trials using as-required OAC. In a short survey of patients with a Reveal LINQ at the John Radcliffe Hospital, 92% were very satisfied and would have a Reveal LINQ purely as a research device.

4. OBJECTIVES AND OUTCOME MEASURES

Objectives	Outcome Measures	Timepoint(s) of evaluation of this outcome measure (if applicable)

Primary Objective To investigate the reduction in oral anticoagulation (OAC) utilisation during follow-up.
	
Primary Outcome Measures Calculate the proportion of time off anticoagulation OAC
	
During follow-up (minimum 13 months)

Secondary Objectives
 
 1. Thromboembolic events (Ischaemic stroke, transient ischaemic attack (TIA) and systemic embolism) 2. Major bleeding 3. Minor bleeding 4. Any stroke (ischaemic, haemorrhagic or undetermined). 5. All-cause mortality 6. Protocol adherence 7. To assess response time from AF episode onset to patient starting as-required OAC 	
Secondary Outcome Measures
 
 1. Calculate the rate of ischaemic stroke, TIA and systemic embolism in patients on as-required OAC 2. Calculate the rate of major bleeding in patients on as-required OAC 3. Calculate the rate of minor bleeding in patients on as-required OAC 4. Calculate the stroke rate (ischaemic, haemorrhagic or undetermined) 5. Calculate the rate of all-cause mortality in patients on as-required OAC 6. Calculate the number of daily transmissions and percentage of patients that restarts OAC within 24 hours of the smartphone-alert. 7. Time from AF episode onset to detection, time to alerts being sent and acknowledged and OAC 	
 1. During follow-up (minimum 13 months) 2. During follow-up (minimum 13 months) 3. During follow-up (minimum 13 months) 4. During follow-up (minimum 13 months) 5. During follow-up (minimum 13 months) 6. During follow-up (minimum 13 months) 7. During follow-up (minimum 13 months)

	being taken by the participant. Proportion of missed AF episodes, transmissions or alerts.	
--	--	--

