it will send an alert to the CareLink™ Network. Our software programme actively screens Carelink every 5 minutes and will generate a patient SMS text message in response to an AF episode. The SMS is sent to the participant advising of the episode, prompting them to restart OAC. They must respond to the notification to acknowledge receipt and confirm they have commenced their OAC. The software will also send an email notification to the research team that the threshold for OAC initiation has been met. If there is no response from the patient within 24 hours, they will receive a second notification. If they do not respond to this second notification, a member of the research team will make direct contact with the patient (within 48 hours of AF episode onset) to ensure they have commenced their OAC and troubleshoot any issues they may be having.

A member of the research team will adjudicate all alerts and contact participants within 48 hours. If the alert was appropriate, participants will be advised to continue OAC for at least 30 days. If, after reviewing the episode, the alert is deemed inappropriate (false positive alert i.e., did not meet criteria for OAC initiation) participants will be instructed to stop OAC and this false positive alert will be logged.

Once OAC is initiated, participants may discontinue OAC if they have 30-day freedom from: 1) any continuous AF episode longer than 60 minutes, and 2) any AF burden of more than 1 hour in a 24-hour period. A member of the research team will contact them by telephone to do so.

[figure not shown]

Figure 4. Study algorithm for the initiation and discontinuation of oral anticoagulation (OAC)

As a safety measure, the LINQ II™ ICMs perform automatic transmissions every 24 hours to CareLink™. The research team will conduct a daily review of all transmissions. If an AF episode/AF burden is identified that meets initiation criteria but failed to trigger an appropriate smartphone alert, participants will be contacted within 24 hours and instructed to restart OAC. Any failure of the system to generate an alert will be reviewed and logged.

During the study (run-in and treatment period), participants will keep a diary of any new drugs started, stopped or dose changes.

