11 STATISTICS AND ANALYSIS

11.1 Analysis of Outcome measures

Descriptive statistics will be reported as count (percentage) for the categorical variables and mean (\pm standard deviation) for the continuous variables. The primary endpoint will be total OAC utilisation, which will be calculated by dividing the total number of days on OAC with the total follow-up duration. Adjudication of all LINQ II™ ICM electrograms will be performed by the research team to determine if notification was appropriate or inappropriate. The percentage of appropriate notifications and the mean time (\pm standard deviation) from notification to taking OAC will be measured. The associations of the measurements with the patient demography, medical history, imaging biomarkers, medications, etc. will be investigated.

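### The restart measure under protocol adherence runs from the smartphone alert, while the protocol's own 24 h target and 48 h limit run from AF onset, and no outcome states the share of events meeting those limits

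*Protocol*

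**What the plan says.** **Alert clock.** Under protocol adherence, the Synopsis gives the "percentage of patients that restart OAC within 24 hours of the smartphone-alert", and Section 4 has the same measure: "percentage of patients that restarts OAC within 24 hours of the smartphone-alert". Section 11.1 names one interval, to be summarised as mean and standard deviation: "from notification to taking OAC will be measured". That interval also starts at the alert.

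**Onset clock.** Section 3 describes "a target for participants to commence OAC within 24 hours of AF onset, and no later than 48 hours". Section 5 says that, after two unanswered notifications, "a member of the research team will make direct contact with the patient (within 48 hours of AF episode onset". Objective 7 is "To assess response time from AF episode onset to patient starting as-required OAC". Its outcome lists the steps from onset through detection and alert to OAC, and the proportion of episodes, transmissions or alerts that were missed. It sets no time threshold.

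**Failed alerts.** Section 5 foresees an event that "meets initiation criteria but failed to trigger an appropriate smartphone alert, participants will be contacted within 24 hours". The safety net is that the monitors "perform automatic transmissions every 24 hours to CareLink", with a daily review by the research team. Alert failures are logged.

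**Other component of outcome 6.** Outcome 6 also counts daily transmissions. That part does not depend on the alert and is not at issue here.

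**The concern.** The outcome labelled protocol adherence uses the same figure, 24 hours, as the protocol's timing target but starts it at a different moment. A reader of the report could easily take one for the other. The 48 h limit appears in no outcome.

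The study asks whether as-required OAC can be delivered through the implanted monitor and automated alerts. The protocol's own yardstick for timely delivery is time since AF onset. A percentage counted from the alert leaves out everything before the alert, and it has no starting point at all when no alert is sent. Following the plan as written, the only thresholded adherence figure could look good while the protocol's stated timing was missed. Outcome 6 also counts patients, although one patient may have several qualifying events and meet the limits in some but not in others.

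**Working it through.** **Inputs (Section 3.1, pilot study, software versions 1.0 to 3.0 combined).** Median detection to alert: 183 min. Median alert to reply: 5.1 min. Median detection to reply: 296.5 min, with 94% of replies within 24 h. One episode took more than 24 h for a reply, and on three occasions there was none. The total number of replies, N, is not given. These replies acknowledged an alert; they were not OAC starts.

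**Step 1: reproduce the protocol's conversions.** 183/60 = 3.05 h (stated as 3.1). 296.5/60 = 4.94 h (stated as 4.9). Both agree.

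**Step 2: latest restart that still passes outcome 6.** Time from onset = time from onset to trigger + delay from detection to alert + 24 h.
- At the median delay, counted from detection: 3.05 + 24 = 27.05 h.
- Adding 1 h from onset to trigger (an assumption, taken from the one-hour initiation criterion): 28.05 h.
- With the same 1 h and assumed alert delays of 0, 6, 12 and 24 h: 25, 31, 37 and 49 h. The last also passes the 48 h limit.

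**Step 3: where the onset limits fall on the alert clock.** With 1 + 3.05 = 4.05 h before the alert, the 24 h target falls 24 − 4.05 = 19.95 h after the alert, and the 48 h limit 48 − 4.05 = 43.95 h after it.
- A restart between 19.95 and 24 h after the alert counts as adherent but misses the target.
- A restart between 24 and 43.95 h after it is not separated from one beyond the limit.

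These are boundaries, not expected frequencies.

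**Step 4: a failed alert.** Up to 24 h to the next automatic transmission, plus contact within 24 h, gives up to 24 + 24 = 48 h before a restart is instructed, even if the transmission is reviewed at once. This event has no start time on the clock of outcome 6. The protocol gives no alert failure rate, and none is assumed.

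**Step 5: can the pilot size the gap?** Suppose the single late reply is counted from the alert and the 94% from detection. The shares beyond 24 h are then 1/N and 6%, and the gap is 0.06 − 1/N.

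| N (assumed) | Gap, percentage points |
|---|---|
| 17 | 0.1 |
| 50 | 4.0 |
| 100 | 5.0 |
| 200 | 5.5 |

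If instead the 94% counts the three non-replies as late, then with N = 67 the share is (67 − 4)/67 = 94.0%, and there is no gap between the clocks. The range is therefore 0 to just under 6 points, and the pilot does not settle it.

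**The case against.** The strongest reply is that outcomes 6 and 7 complement each other: one measures what participants do once told, the other the whole path from onset. A participant cannot act on an alert not yet sent, and Section 3.2 says that the messaging software is not under assessment. How a planned time variable is summarised is often left to the analysis plan. Section 11.1 is brief and does not name the stroke or bleeding rates either, so its silence on onset intervals does not show that they were dropped.

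Much of this stands, and it rules out several stronger conclusions that a reader might draw.
- **That time from onset will go unmeasured, or that failed alerts will go unrecorded.** Outcome 7 covers both, and Section 5 logs alert failures.
- **That outcome 6 as a whole is on the wrong clock.** Only its restart component is.
- **That an event without an SMS reply has no OAC start time.** Section 6.9 makes the reply the time stamp. But Section 5 also has staff contact non-responders to make sure OAC has begun, and it has participants keep a drug diary, which Section 12.1 lists as source data. The diary may give at least a date.
- **That adherence will be clearly overstated.** The pilot range includes zero. It pools software versions that crashed, version 3.0 is expected to be faster, and most replies were prompt.
- **That the delay before the alert drives late starts.** The component medians add to 183 + 5.1 = 188.1 min, while the median total is 296.5 min. The medians do not show which interval produces the late tail.

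What remains is that the protocol itself fixes both the timing standard and the adherence threshold, and they use different clocks. Outcome 7 states no threshold, so an analysis faithful to Section 4 would report the alert-based figure as protocol adherence. The statement in Section 3.2 is a reason to keep an alert-based measure of participant response, but not to make it the only thresholded measure of adherence.

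**Conclusion.** The point holds as a mismatch between passages of the protocol. The restart component of outcome 6 and the interval in Section 11.1 run from the alert. The 24 h target, the 48 h limit and the direct-contact limit run from AF onset. No outcome gives the share of qualifying events meeting the onset-based limits.

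At the pilot median delay the two clocks differ by 3.05 h from detection, or 4.05 h from onset if the trigger takes 1 h. The share of events that would be classified differently cannot be computed from the protocol and may be near zero. Failed-alert events fall outside the threshold whatever their number.

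Severity is minor to moderate. The outcome is secondary and descriptive in a single-arm feasibility study of 50 participants, and the primary endpoint is unaffected. No view is taken on which time limit is clinically right.

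**What to change.** Reconcile the passages so that the adherence outcome and the timing standard refer to each other.

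- Keep the alert-based percentage, labelled as a measure of participant response, beside the outcome 7 intervals.
- Add to outcome 6 or 7, and to Section 11.1, the proportion of adjudicated qualifying events with confirmed OAC start within the protocol's stated 24 h and 48 h of onset. Count events that arise in the treatment period while the participant is off OAC. For events that qualify on daily burden, say which moment counts as onset.
- Keep failed alerts and non-replies in the denominator. Take the start time from the SMS reply, direct contact or diary, and record which source was used.

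**Cost.** Wording changes and slightly more analysis. Outcome 7 already calls for the onset, alert, acknowledgement and OAC times. The one added item is to record the OAC start time at direct contact. The reported adherence may look less favourable.
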